4.6 GUIDELINES FOR IBRUTINIB DOSAGE WITH SURGICAL PROCEDURES

Ibrutinib may increase risk of bleeding with invasive procedures or surgery. The following guidance should be applied to the use of ibrutinib in the perioperative period for subjects who require surgical intervention or an invasive procedure while receiving ibrutinib.

4.6.1 Minor Surgical Procedures

For minor procedures (such as a central line placement, skin or needle biopsy, lumbar puncture [other than shunt reservoir access], thoracentesis, or paracentesis) ibrutinib should be held for at least 3 days prior to the procedure and should not be restarted for at least 3 days after the procedure. For bone marrow biopsies that are performed while the subject is on ibrutinib, it is not necessary to hold ibrutinib.

4.6.2 Major Surgical Procedures

For any surgery or invasive procedure requiring sutures or staples for closure, ibrutinib should be held at least 7 days prior to the intervention and should be held at least 7 days after the procedure and restarted at the discretion of the investigator when the surgical site is reasonably healed without serosanguineous drainage or the need for drainage tubes.

4.6.3 Emergency Procedures

For emergency procedures, ibrutinib should be held as soon as possible and until the surgical site is reasonably healed or for at least 7 days after the urgent surgical procedure, whichever is longer.

5 CORRELATIVE STUDIES FOR RESEARCH

5.1 BIOSPECIMEN COLLECTION

Test/assay	Volume blood (approx.)	Type of tube^{Error!} Reference source not found.	Collection point (+/- 48hrs)	Location of specimen Storage
Immune monitoring and Biomarker Studies	50 ml	Five 10 ml green top (heparin) tubes	C1D1, C4D1, C7D1, C12D28	Clinical Pharmacology Blood Processing Core (BPC), [name].
IHC for myofibroblast markers	oral/skin biopsy (optional), NIH site only	N/A	Baseline, Cycle 7 Day 1, Cycle 12 Day 28	Clinical Pharmacology Blood Processing Core (BPC), [name].
PK (pre & post)	6 ml	Sodium Heparin	C1D15	Clinical Pharmacology Blood Processing Core (BPC), [name].

^a Please note that tubes and media may be substituted based on availability with the permission of the PI or laboratory investigator.

5.1.1 Immune Monitoring and Biomarker Studies

Peripheral blood will be collected for cGVHD cell phenotypes, gene expression (Section 5.3) and plasma biomarker assays at 4 time points, concurrent with clinical evaluation of chronic GvHD: at C1D1 (start of ibrutinib treatment), C4D1 (3 months), C7D1 (6 months), and C12D28 (12 months).

At each time point collect 50 ml of blood (e.g., 5, 10 ml green top tubes) in heparinized tubes as plasma. Store plasma at -80° C in at least 4 vials containing aliquots of 1ml of plasma. Process the remaining blood with Lymphocyte Separation Medium to collect PBMC. Aliquot the cells into at least 2 vials at 10 million PBMC/vial (if less than 20 million total cells, divide equally into 2 tubes). Cryopreserve in liquid nitrogen vapor phase.

All vials are to be labeled with a bar code. The bar codes will be linked by participating site to a spreadsheet in which participant biospecimens are identified by Unique Participant Number, study calendar timepoint and either total cell number or plasma volume in each vial. Dates of collection and any relevant notes of the biospecimen collection (such as anti-coagulant, processing delays) will be noted. PBMC and plasma will be sent to NCI for testing at the

completion of accrual for the trial or at intermediate timepoints to be agreed upon. Send to the Clinical Pharmacology Blood Processing Core (BPC) of the National Cancer Institute, NIH in Bethesda MD.

Notify [name] and [name] at least 24 hours prior to shipping cryopreserved materials. Include the spreadsheet of samples to be shipped in the email and in the shipment. Ship cryopreserved cells and plasma on dry ice to: Attention [name] and [name], BPC Lab, [name]. Shipments can only be received on Tuesday through Thursday.

Multiparameter flow cytometry assays may include, but not be limited, to the following markers:

1. Assessments of lymphocyte populations including CD3+, CD3+CD4+ and CD3+CD8+ Tcells, CD19+ B cells, and CD3-CD56+ NK cells
2. Assessments of B cell subsets to identify frequencies of transitional, naive, preGC, memory, tissue memory and regulatory subsets: (marker panel will include CD19, CD20, IgD, CD27, CD38, CD21, CD10, CD24, CD3)
3. Assessments of T cell subsets to identify naive, Tscm, central memory, effector memory, TEMRA, regulatory cells (marker panel will include CD3, CD4, CD8, CD25, CD127, CCR7, CD45RA, CD27, CD95)
4. Assessments of T helper lineages by transcription factors (marker panel will include CD3, CD4, CD8, Tbet, RORgt, GATA3, FoxP3).

Plasma biomarker ELISA assays may include but not be limited to the following currently proposed biomarkers of CGVHD: ST2, CXCL10, BAFF, IL-6, TNF, IFNg. Additional or alternative plasma factors will be considered based upon relevant CGVHD biomarkers identified by the end of biospecimen accrual.

5.1.2 Oral/Skin Biopsy

An optional research biopsy of involved or unininvolved skin or oral mucosa will be offered to participants for assessment of sclerotic or lichen-planus like disease by H&E and pathologist evaluation. Immunohistochemistry methods will be applied to look for myofibroblast markers and pSMAD in the sclerotic skin, for T-cell infiltrates, and IFN-induced factors in the oral mucosa and erythematous skin. The advantage of histology is the greater amount of information on cell populations and functional changes *in situ* of the disease. These biopsies will be obtained by one of the study investigators and processed and stored at the BPC Lab. A biopsy sample will be also sent to the NCI pathology laboratory. Biopsies will only be performed at the NIH site. See the Study Calendar in [Appendix K](#) for collection timepoints.

5.2 Pharmacokinetic Studies

Blood samples for the determination of sparse steady-state plasma concentrations of ibrutinib will be obtained from each participant on a scheduled visit at the C1D15 visit. Participants will fast the night prior to the visit, have a pre-dose (trough) sample drawn, take the dose, then have another sample drawn 90-min post (+/- 10min) based on a peak that occurs 1-2 hr. post dose (Ibruvica® package insert). Blood will be collected into a 6mL sodium heparin tube (BD, Franklin Lakes, NJ). Bioanalytical measurements on plasma collected at both the NIH site and

participating sites will be conducted on an ultra HPLC-MSMS system using an assay developed and validated by the NCI Clinical Pharmacology Program.

The PK sampling will be used to monitor ibrutinib exposure in order to correlate to clinical response and toxicity.

5.1.2.1 Handling and Processing of Specimens

The samples will be placed immediately on wet ice and refrigerated. The date and exact time of each blood draw should be recorded on the sample tube and the PK sheet. In participants treated at the non-NIH sites, tubes will be centrifuged promptly after collection to separate off plasma. Plasma will be cryopreserved for storage at -80°C. PK samples will be labeled so as to distinguish them from immune monitoring and biomarker samples. At the end of the trial (or at intermediate points to be determined), PK plasma will be shipped on dry ice to the Blood Processing Core of the Clinical Pharmacology Program at the NCI, along with a spreadsheet key identifying protocol, participant, date, stage (pre-dose or 90min), time of draw and time of processing.

Please e-mail [contact] at least 24 hours before transporting samples (the Friday before is preferred).

For sample pickup, page [name].

For immediate help, call [contact] (main blood processing core number) or, if no answer, [contact] (main clinical pharmacology lab number).

For questions regarding sample processing, contact [contact].

The samples will be processed, barcoded, and stored in [name] lab until requested by the investigator.

5.2 SAMPLE STORAGE, TRACKING AND DISPOSITION

Samples will be ordered in CRIS and tracked through a Clinical Trial Data Management system for NIH. Should a CRIS screen not be available, the CRIS downtime procedures will be followed. Samples will not be sent outside NIH without appropriate approvals and/or agreements, if required.

5.2.1 Samples Managed by [name] Processing Core (BPC)

5.2.1.1 Sample Data Collection

All samples sent to the Blood Processing Core (BPC) will be barcoded, with data entered and stored in Labmatrix utilized by the BPC. This is a secure program, with access to Labmatrix limited to defined [name] lab personnel, who are issued individual user accounts. Installation of Labmatrix is limited to computers specified by [name]. These computers all have a password restricted login screen.

Labmatrix creates a unique barcode ID for every sample and sample box, which cannot be traced back to participants without Labmatrix access. The data recorded for each sample includes the participant ID, name, trial name/protocol number, time drawn, cycle time point, dose, material type, as well as box and freezer location. Participant demographics associated with the clinical center participant number are provided in the system. For each sample, there are notes associated with the processing method (delay in sample processing, storage conditions on the ward, etc.).

5.2.1.2 Sample Storage

Barcoded samples are stored in barcoded boxes in a locked freezer at either -20 or -80°C according to stability requirements. These freezers are located onsite in the BPC and offsite at NCI Frederick Central Repository Services in Frederick, MD. Visitors to the laboratory are required to be accompanied by laboratory staff at all times.

Access to stored clinical samples is restricted. Samples will be stored until requested by a researcher named on the protocol. All requests are monitored and tracked in Labmatrix. All researchers are required to sign a form stating that the samples are only to be used for research purposes associated with this trial (as per the IRB approved protocol) and that any unused samples must be returned to the BPC. It is the responsibility of the NCI Principal Investigator to ensure that the samples requested are being used in a manner consistent with IRB approval.

5.2.2 BPC Sample Storage, Tracking and Disposition

Participant blood and tissue samples, collected for the purpose of research under IRB approved protocols of the Blood and Inherited Diseases Cellular Therapy Program (BID-CTP) may be archived by the Clinical Pharmacology Blood Processing Core (BPC), [name]. All data associated with archived clinical research samples is entered into Labmatrix. Access is limited to BPC staff and BID-CTP clinical staff, requiring individual login and password.

The data recorded for each sample includes the participant ID, trial name/protocol number, date drawn, treatment cycle/post-transplant time point, cell source (e.g. peripheral blood, marrow,) as well as box and freezer location. Participant demographics that correlate treatment outcomes and therapies with the samples can be obtained only through the NCI clinical records. As of January 2007, all newly received samples receive a unique bar code number, which is included in the sample record in the BPC database. Only this bar code is recorded on the sample vial and the vials will not be traceable back to participants without authorized access to the BPC database. All non-coded samples previously archived will be stripped of identifiers prior to distribution for any use other than as a primary objective of the protocol under which they were collected.

Samples are stored in freezers. All samples will be labeled solely with a bar code (which includes the date, and serially determined individual sample identifier). The key will be available to a restricted number of BID-CTP investigators and associate investigators on the protocol. Coded samples will be stored frozen at -20°, -80° or liquid nitrogen vapor phase to -180 C according to the stability requirements in a single location under the restricted control of the BPC lab.

These freezers are located onsite at the Clinical Pharmacology Blood Processing Core (BPC) laboratory (5A08) (-85°C freezer) Access to samples from a protocol for research purposes will be by permission of the Principal Investigator of that protocol in order to be used (1) for research purposes associated with protocol objectives for which the samples were collected, or (2) for a new research activity following submission and IRB approval of a new protocol and consent, or (3) for use only as unlinked or coded samples under the OHSRP Exemption Form guidelines stipulating that the activity is exempt from IRB review. Unused samples must be returned to the BPC laboratory. Samples, and associated data, will be stored permanently unless the participant withdraws consent. If researchers have samples remaining once they have completed all studies associated with the protocol, they must be returned to the BPC laboratory.

Once research objectives for the protocol are achieved, researchers can request access to remaining samples, providing they have both approval of the Principal Investigator of the original protocol under which the samples or data were collected and either an IRB approved protocol and participant consent or an OHSRP exemption indicating that the activity is exempt from IRB review.

The BPC will report to the Principal Investigator any destroyed samples, if samples become unsalvageable because of environmental factors (ex. broken freezer or lack of dry ice in a shipping container), lost in transit between facilities or misplaced by a researcher.

5.2.3 Protocol Completion/Sample Destruction

All specimens obtained in the protocol are used as defined in the protocol. Any specimens that are remaining at the completion of the protocol will be stored in the conditions described in sections above. The study will remain open so long as sample or data analysis continues. Samples from consenting subjects will be stored until they are no longer of scientific value or if a subject withdraws consent for their continued use, at which time they will be destroyed. If the participant withdraws consent the participant's data will be excluded from future distributions, but data that have already been distributed for approved research use will not be able to be retrieved.

The PI will record any loss or unanticipated destruction of samples as a deviation. Reporting will be per the requirements of section [7.2](#).

5.3 SAMPLES FOR GENETIC/GENOMIC ANALYSIS

Multiplex gene expression assays: Based upon studies utilizing peripheral blood monocytes as 'reporter' cells for the operant processes of CGVHD (53), CD14+ monocytes will be bead sorted from one vial of cryopreserved PBMC, and the isolated RNA will be assessed for expression of a panel of genes to include but not necessarily be limited to the following: Pattern Recognition Receptors (TLR, CLR, NLR and RLR receptors), Interferon-induced genes, genes involved in monocyte migration and genes induced by glucocorticoids. The custom Nanostring probe panels will be assessed using nCounter Systems analyses and analyzed using nSolver software.

6 DATA COLLECTION AND EVALUATION

6.1 DATA COLLECTION

The site PI will be responsible for overseeing entry of data into a 21 CFR Part 11 compliant data capture system provided by the NCI CCR and ensuring data accuracy, consistency and timeliness. The principal investigator, associate investigators/research nurses and/or a contracted data manager will assist with the data management efforts. Primary and final analyzed data will have identifiers so that research data can be attributed to an individual human subject participant.

The subject's relevant medical history will be collected and recorded. Baseline medical signs and symptoms must be documented to establish baseline severities. A disease history and the date of initial diagnosis should be recorded.

Newly diagnosed moderate or severe chronic GvHD via Chronic GvHD Assessment performed at screening should be documented.

Any clinically significant abnormalities noted at ECG during screening should be documented.

Dose changes must be recorded in the Dose Administration eCRF.

Abbreviated Title: Ibrutinib for Chronic GvHD

Version Date: 4/26/2023

All medications (prescription and non-prescription), including topical chronic GvHD therapies taken throughout the study must be recorded on the appropriate page of the CRF.

All adverse events, including clinically significant abnormal findings on laboratory evaluations, regardless of severity, will be followed until return to baseline or stabilization of event. Grade 1 adverse events will not be recorded as they are not expected to be clinically significant.

Document AEs from the first study intervention, Study Day 1 of Cycle 1 through 30 days after the subject received the last study drug administration. Beyond 30 days after the last intervention, only adverse events which are serious and related to the study intervention need to be recorded.

New malignant tumors including solid tumors, skin malignancies and hematologic malignancies will be recorded for the duration of study treatment and during follow-up period.

An abnormal laboratory value will be recorded in the database as an AE **only** if the laboratory abnormality is characterized by any of the following:

- Results in discontinuation from the study
- Is associated with clinical signs or symptoms
- Requires treatment or any other therapeutic intervention
- Is associated with death or another serious adverse event, including hospitalization.
- Is judged by the Investigator to be of significant clinical impact
- If any abnormal laboratory result is considered clinically significant, the investigator will provide details about the action taken with respect to the test drug and about the participant's outcome.

End of study procedures: Data will be stored according to HHS, FDA regulations, and NIH Intramural Records Retention Schedule as applicable.

Loss or destruction of data: Should we become aware that a major breach in our plan to protect subject confidentiality and trial data has occurred, this will be reported expeditiously per requirements in section [7.2.1](#).

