4.4.2 Antiplatelet Agents and Anticoagulants

Use ibrutinib with caution in subjects requiring anticoagulants or medications that inhibit platelet function. In an in vitro platelet function study, inhibitory effects of ibrutinib on collagen induced platelet aggregation were observed.

Supplements such as fish oil and vitamin E preparations are recommended to be avoided during treatment with ibrutinib.

Bleeding events of any grade, including bruising and petechiae, occurred in subjects treated with ibrutinib. Subjects with congenital bleeding diathesis have not been studied. Ibrutinib should be

held at least 3 to 7 days pre- and post-surgery depending upon the type of surgery and the risk of bleeding (see Section [4.6](#)).

Subjects requiring the initiation of therapeutic anticoagulation therapy (e.g., atrial fibrillation) should be monitored closely for signs and symptoms of bleeding and the risks and benefits of continuing ibrutinib treatment should be considered.

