8.1.6 Adverse Events of Special Interest (AESI)

8.1.6.1 Major Hemorrhage

Major hemorrhage is defined as any of the following:

- Any treatment-emergent hemorrhagic adverse events of Grade 3 or higher*
- Any treatment emergent serious adverse events of bleeding of any grade
- Any treatment-emergent central nervous system hemorrhage / hematoma of any grade

*All hemorrhagic events requiring transfusion of red blood cells should be reported as grade 3 or higher AE per CTCAE v5.0

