8.3 REPORTING OF SERIOUS ADVERSE EVENTS

Any AE that meets protocol-defined serious criteria or meets the definition of Adverse Event of Special Interest that require expedited reporting must be submitted immediately (within 24 hours of awareness) to OSRO Safety using the CCR SAE report form.

All SAE reporting must include the elements described in Section [8.1.6.1](#).

SAE reports will be submitted to the Center for Cancer Research (CCR) at:

[contact] and to the CCR PI and study coordinator. CCR SAE report form and instructions can be found at:

<https://ccrod.cancer.gov/confluence/display/CCRCRO/Forms+and+Instructions>

Following the assessment of the SAE by OSRO, other supporting documentation of the event may be requested by the OSRO Safety and should be provided as soon as possible.

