10.4.4 Safety analyses

Safety of the agent will be assessed by determining the grade of adverse events noted in each participant, and reporting the fraction with grade 3 and grade 4 adverse events. Participants who receive at least one dose of the study treatment will be evaluable for safety. Safety data will be presented in a summary. The safety data will consist of the reporting of all adverse events, and may also include reporting vital signs, physical examination data, and laboratory safety data.

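### The rule against recording grade 1 events has no exception, so a non-serious grade 1 CNS hemorrhage, which the protocol itself classes as major hemorrhage, can be missing from the adverse event data

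*Combined protocol and SAP*

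**What the plan says.** Section 6.1 (Data Collection) sets the recording threshold: "Grade 1 adverse events will not be recorded as they are not expected to be clinically significant". No exception is attached for serious events or events of special interest. The sentence just before it says that all adverse events, "regardless of severity, will be followed until return to baseline or stabilization of event".

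Section 8.1.6.1 defines major hemorrhage, the only adverse event of special interest in the protocol. The definition has three limbs: treatment-emergent bleeding of grade 3 or higher; "Any treatment emergent serious adverse events of bleeding of any grade"; and "Any treatment-emergent central nervous system hemorrhage / hematoma of any grade".

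Section 8.2 requires serious adverse events, with no grade limit, to go on the serious event form, into the medical record and into the clinical database. It has no matching instruction for special-interest events that are not serious.

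Section 8.3 covers any event that is serious or that "meets the definition of Adverse Event of Special Interest that require expedited reporting must be submitted immediately (within 24 hours of awareness) to OSRO Safety".

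Section 10.4.4 plans "reporting the fraction with grade 3 and grade 4 adverse events" and adds: "The safety data will consist of the reporting of all adverse events".

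**The concern.** The reason that Section 6.1 gives for dropping grade 1 events is that they are not expected to matter clinically. Section 8.1.6.1 takes the opposite view for one kind of event, since it treats a CNS bleed as major hemorrhage however low its grade. Site staff who follow Section 6.1 literally would leave out an event that another section singles out for attention.

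Section 10.4.4 then describes the safety report as covering all adverse events, which the data cannot support if grade 1 events were never entered. Safety is a secondary objective (Section 1.1), and Section 1.2.2.4.1 names intracranial hemorrhage among the major bleeding events seen with ibrutinib. An event that was not recorded when it happened may be hard to recover at analysis.

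**Working it through.** No sample size, error rate or event count is in dispute, so this is a comparison of text. The steps are to split CNS hemorrhage by grade and seriousness, and to ask of each cell which limb of Section 8.1.6.1 covers it, whether Section 6.1 records it, and whether another section puts it in the database.

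| CNS hemorrhage | Limb of 8.1.6.1 | Recorded under 6.1? | Other database instruction |
|---|---|---|---|
| Grade 3 or higher | First and third (second also, if serious) | Yes | 8.2 if serious |
| Grade 2, serious | Second and third | Yes | 8.2 |
| Grade 2, not serious | Third only | Yes | None needed |
| Grade 1, serious | Second and third | No, as worded | 8.2 |
| Grade 1, not serious | Third only | No | None stated |

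1. The first two limbs already cover every CNS bleed that is grade 3 or higher or serious. What the third limb adds is the non-serious grade 1 and grade 2 CNS bleed.

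2. Section 6.1 takes the grade 1 part of that addition back out. This is the last row, the only cell in which a defined special-interest event has no stated way into the database.

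3. In the fourth row Sections 6.1 and 8.2 disagree on their face. Section 8.2 is the specific instruction for serious events, so those events should be captured.

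4. For the last row, Section 8.3 is the only remaining route, and its wording can be read in two ways. Either every special-interest event goes to the sponsor's safety office within 24 hours, or only the subset that needs expedited reporting does, and the protocol does not define that subset. Even on the wider reading, Section 8.3 is a report to the safety office and does not say that the event enters the trial's adverse event data.

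5. The two statistics in Section 10.4.4 behave differently. The grade 3 and grade 4 fractions use no grade 1 events and do not change. The statement that all adverse events are reported is wider than what Section 6.1 collects.

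6. On frequency, the documents give no rate for non-serious grade 1 CNS hemorrhage. The nearest figures are subdural hematoma leading to discontinuation in 0.6% of 1,600 monotherapy subjects (Section 1.2.2.2) and serious related subdural hematoma in 15 of 4,791 (Section 16.13, Appendix L). The first counts events that stopped treatment and the second counts serious events, so neither sizes the exposed cell.

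**The case against.** The strongest reply is that leaving out grade 1 events is a deliberate choice with a stated reason, and that other provisions cover what matters. Serious events reach the database at any grade. Section 8.1.2 lets an investigator class an important medical event as serious without a hospital admission, which could bring many CNS bleeds into the serious-event route. Section 8.3 may carry the rest to the sponsor. The promise in Section 10.4.4 can also be read as all events collected under Section 6.1.

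Most of this stands. Not recording routine grade 1 events is a legitimate choice, and nothing here asks for it to be reversed. The reply narrows the gap to the non-serious grade 1 CNS bleed but does not close it: classing such an event as serious is left to judgment, and no section states its database entry. The milder reading of Section 10.4.4 is reasonable, but the section does not say so.

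Three stronger readings are tempting and should not be drawn:

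- A reader might infer that the planned count of special-interest events will be too low. Section 10.4.4 plans no such count.
- A reader might infer that every such bleed is certainly an expedited report under Section 8.3. The qualifier in that section leaves this open.
- A reader might infer that the drug's bleeding signal as a whole is understated, since Section 4.4.2 says "Bleeding events of any grade, including bruising and petechiae, occurred in subjects treated with ibrutinib" and Section 1.2.2.3 gives bruising in 24% of the earlier chronic GvHD study. Non-serious grade 1 bruising is not a special-interest event, the documents give no grade split for that 24%, and bleeding that is grade 2 or higher or serious is still recorded. No number of missing bruising events can be derived.

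**Conclusion.** The contradiction is real and should be corrected, but its reach is small. As written, Section 6.1 keeps a non-serious grade 1 CNS hemorrhage out of the adverse event data although Section 8.1.6.1 calls it major hemorrhage, and Section 10.4.4 describes a fuller report than the collection rule allows.

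The size cannot be given as a number. That such events would be rare is a judgment and not a figure from the documents. The primary endpoint, the two-stage design and the grade 3 and grade 4 fractions are unaffected.

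The conclusion assumes that sites apply Section 6.1 literally and that Section 8.2 prevails for serious events. If the case report form or its completion guide already exempts special-interest events, the gap is one of wording only; the documents do not show this.

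**What to change.** Make two changes of wording.

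- **Section 6.1:** keep the rule that grade 1 events are not recorded, but except events that meet the special-interest definition in Section 8.1.6 or the criteria for a serious event. State that these are entered in the clinical database at any grade.
- **Section 10.4.4:** describe the safety data as all recorded adverse events, meaning grade 2 or higher, plus special-interest and serious events of any grade.

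This settles the conflict without asking sites to collect minor bleeding at every grade, which would be a new requirement beyond what the contradiction calls for. The cost is a protocol amendment, which the Statement of Compliance says the IRB must approve before it takes effect, and a few extra entries. If participants have already been treated, source records should be checked once for any CNS bleed left out under the present wording.
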